- Incorporation of therapy advances that emerge before or during the study. The SC group may not use a CGS device during the 9-month randomization phase except in the blinded 7-day CGS use periods.
- *A "rescue procedure" will be employed for any youth whose HbA_{1c} remains above 9% for 2 consecutive visits or whose HbA_{1c} increases by more than 1.0% over baseline or who has more than one episode of severe hypoglycemia. As would typify clinical practices with similar patients, this will consist of offering monthly clinic visits with a diabetes nurse, weekly telephone consultation with the nurse and referral to a dietitian, social worker, psychologist or psychiatrist at the discretion of the treating endocrinologist.*

Patients randomized to SC will be treated as above but they will not use a CGS during the 9-month Randomized Phase. Given the enrollment criteria for this study, a baseline mean HbA_{1c} for this group can be expected to be about 8.8% and we anticipate a 0.2% increase (~0.15 SD) to about 9.0% during the 9-month randomization phase of the study.

All study participants will receive the above SC regimen. CGS and CGS+BT regimens will differ as below.

Continuous Glucose Sensor (CGS) With consultation from the diabetes team, patients randomized to CGS will select a CGS device for use during the study from among those that can be made available for use in this study. Appropriate training and counseling will be provided by the diabetes nurse to include:

- Parents and youths will be carefully trained in the safe and proper use of the selected CGS device and associated analytic software. *Substantial emphasis will be placed on making treatment decisions suggested by CGS results only after a confirmatory SMBG check is done. CGS use will be portrayed as a supplement to SMBG, not a replacement.* ¹⁴⁹ Training will cover real-time and retrospective analysis of CGS data and appropriate responses to alarms, using a book by H. [name]. ¹⁵⁰ and the JDRF website "Continuous Glucose Monitoring Classroom" that will soon be available for public access.
- Weekly phone contact initiated by the diabetes nurse during the first month of CGS use.
- 24-hour telephone access to an on-call pediatric endocrinologist.
- Week-day telephone access to the diabetes nurse to report device-related problems.

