- A 2-week follow-up visit with the diabetes nurse to download the CGS device and further education about responding to CGS data prospectively and retrospectively. Clinical insulin dose adjustment algorithms previously developed and validated in DirecNet studies will be taught to adolescents and parents. A JDRF website will soon be available that will offer additional teaching materials and supports designed for patients using CGS as a component of diabetes management.
- A 1-month follow-up visit with the diabetes nurse to review the family's use of the insulin adjustment algorithms and to evaluate the need for individual refinement of the algorithms.

- The diabetes nurse will be permitted to bring selected adolescents and parents in for interim clinic visits as needed for remedial education to ensure that the adolescent and parent have the requisite knowledge and skills required for deriving optimal benefit from use of the CGS.

Based on the DirecNet Navigator pilot study, we expect HbA_{1c} to decline by approximately 0.3 SD over 9 months to a mean value of about 8.4% for this group.

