5.13. Sample size and statistical power. Power analysis and sample size estimation were based on projected treatment effects on HbA_{1c}, the primary outcome measure, as shown in the figure below. To estimate sample sizes needed in the three groups for sufficient statistical power, a Monte Carlo simulation study was conducted using MPlus (Version 5).¹⁶⁴ The Monte Carlo procedure is the most common and the preferred methodology to estimate sample size in Individual Growth Modeling.¹⁶⁷⁻¹⁶⁸ In a Monte Carlo study, random samples are generated repeatedly using the known population parameters with a specified sample size. The percentage of simulated samples that have reached significance on the parameters is the estimated power of the study. Thus, the required sample size can be determined accurately by varying sample sizes in a series of simulations. MPlus provides extensive facilities for conducting Monte Carlo studies on IGM. Our simulation study followed the procedures recommended by Muthen & Muthen,^{164, 168} including generating missing values to reflect expected attrition and the pattern of missing data in the proposed study. The primary contrast of interest in this study is change in HbA_{1c} relative to baseline values among adolescents in the SC,

CGS, and CGS+BT groups. Based on the mean HbA_{1c} obtained in several prior trials at Nemours Children's Clinic in Jacksonville and the stated enrollment criteria, we expect that the baseline mean and standard

deviation values will be approximately $8.8\% \pm 1.2\%$. The standard deviation of HbA_{1c} will increase gradually with each measure spaced about 3 months. At the end of 12 months, we expect a 0.8% difference in HbA_{1c} between the CGS and CGS+BT groups. Assuming a standard deviation of approximately 1.5% at the end of the study, the effect size will be 0.533, a moderate effect size as defined by Cohen¹⁶⁹ that is clearly clinically significant. Based on the retention rates in our NIH-funded randomized trials, we anticipate an attrition rate <10% during the 1-year study. Therefore, enrollment of 150 patients (50 per group) should result in at least 135 (45 per group) at the end of the 9-month randomization phase of the study. We anticipate that about 120 participants (40 per group) will complete the 3-month Continuation Phase of the study.

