Based on these parameters with 5 equally spaced measures of HbA_{1c} (Baseline, 3, 6, 9, and 12 months) and random missing values, the Monte Carlo study with 3000 simulated samples showed that the power of the design is 94.5%. Muthen and Muthen^{164, 168} also recommend that the parameter bias should not exceed 10% and standard error bias should not exceed 5%. All of these criteria were satisfied in the Monte Carlo study. A similar Monte Carlo study was conducted for estimating the statistical power contrasting the SC and CGS groups. We expect a mean difference of approximately 0.6% in HbA_{1c} between the two groups at the end of the study. The Monte Carlo study showed with 50 participants in each group and approximately 10% missing values, the statistical power remains above 80%. Fan¹⁶⁷ compared the statistical power between IGM and the traditional Repeated Measures ANOVA with longitudinal data under different situations. Fan's conclusion was that IGM consistently showed higher power than Repeated Measures ANOVA to compare group differences in change over time. Since we will apply IGM to the evaluation of all three primary hypotheses, we are confident that the planned sample size offers sufficient statistical power in this study.

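### If the two simulations in section 5.13 share their inputs, 94.5% power for a 0.8% HbA1c difference implies about 76% power for 0.6%, not above 80%

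*Combined protocol and SAP*

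**What the plan says.** Section 5.13 bases the sample size on simulated growth models and defines power in this way: "The percentage of simulated samples that have reached significance on the parameters is the estimated power of the study". No significance level or sidedness is given.

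- **CGS+BT versus CGS.** The effect is "At the end of 12 months, we expect a 0.8% difference in HbA_{1c} between the CGS and CGS+BT groups". The SD is 1.2% at baseline and about 1.5% at the end, with five HbA1c measures to month 12 and random missing values at an unstated rate. The result is "the Monte Carlo study with 3000 simulated samples showed that the power of the design is 94.5" per cent.
- **SC versus CGS.** This run is introduced as similar to the first. Its effect is "We expect a mean difference of approximately 0.6% in HbA_{1c} between the two groups at the end of the study", and its result is "The Monte Carlo study showed with 50 participants in each group and approximately 10% missing values, the statistical power remains above 80" per cent. No SD, variance components or visit schedule are given for it.

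On retention, section 5.13 expects 45 per group at month 9 and about 40 per group at month 12.

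Section 5.8 gives the projected means behind the second contrast. For SC, "we anticipate a 0.2% increase (~0.15 SD) to about 9.0% during the 9-month randomization phase of the study". For CGS, "we expect HbA_{1c} to decline by approximately 0.3 SD over 9 months to a mean value of about 8.4% for this group".

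**The concern.** With sample size, schedule, variances and missingness held fixed, the power of a slope contrast depends only on the size of the effect. One power figure therefore fixes the other, and the two printed figures do not match on that basis.

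SC versus CGS asks whether the sensor alone helps. It falls within Specific Aim 1 and is one of the contrasts listed in section 5.12. Section 5.13 relies on both figures when it concludes that the sample size is sufficient. On the shared-input reading, the chance of missing the assumed sensor effect is about 24% (21–23% with unequal missingness) instead of under 20%. Any multiplicity adjustment, which section 5.9 promises, would lower the power further.

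**Working it through.** **Inputs.** From section 5.13: differences of 0.8% and 0.6%; 50 per group; SD 1.2% rising to 1.5%; visits at 0, 3, 6, 9 and 12 months; 94.5% power from 3000 samples; about 10% missing in the second run. Assumed: two-sided 5%.

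**1. The plan's 94.5%.** It cannot be reproduced exactly, because the within-patient correlation and slope variance are not printed.

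- A plain comparison of month-12 means (0.8%, SD 1.5%, 50 per group, two-sided 5%) gives 76.0%. That is not the planned analysis, and its closeness to the result in step 2 is a coincidence.
- A linear growth model with random intercept and slope, variance rising from 1.2² = 1.44 to 1.5² = 2.25, and 10% or 20% monotone loss gives about 70% to over 99%, depending on the unstated parameters. With 80–90% of baseline variance in the intercept and no intercept–slope correlation, it gives about 92–97%.

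So 94.5% is attainable, and it is taken as given below.

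**2. Carrying it to 0.6%.** The noncentrality is the difference divided by its standard error, and the standard error does not depend on the difference.

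- At 0.8%: z(0.975) + z(0.945) = 1.960 + 1.598 = 3.558.
- At 0.6%: 3.558 × 0.6/0.8 = 2.669.
- Power: Φ(2.669 − 1.960) = Φ(0.709) = 76.1%.

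**3. What 80% would need.** The required noncentrality is 1.960 + 0.842 = 2.802.

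- Difference detectable with the same standard error: 0.8 × 2.802/3.558 = 0.63%.
- Extra information needed at 0.6%: (2.802/2.669)² = 1.10, about 10% more.
- Power at 0.8% if power at 0.6% were exactly 80%: Φ(2.802/0.75 − 1.960) = 96.2%. This is 1.7 points above the printed value. The Monte Carlo standard error is √(0.945 × 0.055/3000) = 0.42 points, so the gap is about four standard errors.

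**4. Sensitivity of the 0.6% power.** Each row starts from 94.5% at 0.8%.

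| What is changed | Power at 0.6% |
|---|---|
| Nothing | 76.1% |
| Monte Carlo error (93.7–95.3% for the first figure) | 74.5–77.8% |
| One-sided 5% | 78.4% |
| Two-sided 2.5%; two-sided 5%/3 | 73.8%; 72.6% |
| First run 20% loss, second 10% | 77–79% |
| The same, with the first figure at its upper limit of 95.3% | 79–81% |
| Second run with no missing data | 79–82% |
| 0.6% reached at month 9, five visits, same missingness | 94.5% |
| 0.6% reached at month 9, four visits to month 9 | 72–91% |

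The unequal-loss row uses standard-error ratios of 1.01–1.04 from the growth models: Φ(2.669 × 1.01 − 1.960) = 77% and Φ(2.669 × 1.04 − 1.960) = 79%. The next row replaces 2.669 by 3.635 × 0.75 = 2.726. The no-missing-data row conflicts with the 10% that section 5.13 states. The month-9 rows follow because 0.6/9 = 0.8/12 = 0.067 per month, so the two slopes are equal.

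**The case against.** A reader might infer that the two powers cannot both be true, or that the claimed power is not delivered. The documents do not support that, for these reasons.

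- **The shared inputs are inferred.** Section 5.13 attaches the 1.5% SD to CGS+BT versus CGS and does not repeat it for SC versus CGS. Section 5.8 equates 0.2% with about 0.15 SD and a fall from 8.8% to 8.4% with about 0.3 SD. Both imply an SD near 1.33 (0.2/0.15 and 0.4/0.3). Crude scaling then gives Φ(2.669 × 1.5/1.33 − 1.960), about 85%. Nothing shows that this SD was used, but nothing fixes 1.5 either.
- **The 0.6% may be a month-9 difference.** The section 5.8 means differ by 9.0 − 8.4 = 0.6% at month 9. On that reading both figures can hold, and a restriction to nine months need not lower the power. Against this, section 5.13 places the 0.6% at the end of the study, words it also uses for the SD in the month-12 calculation. A five-visit model would then give 94.5%, an odd result to report as above 80%.
- **The margin is small.** A difference of 0.63% fits within approximately 0.6%, and unequal missingness combined with the upper Monte Carlo limit just reaches 80%. Scaling by completers alone (45 against 40) gives 80.8%, but it treats dropouts as contributing nothing, whereas section 5.12 uses all available measurements.
- **The contrast is not in Hypothesis 1**, which compares CGS+BT with SC and with CGS. It is nevertheless within Aim 1, and its power is relied on.

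The figure of projected effects to which section 5.13 refers was not available in the text reviewed and may settle the time point. These objections make the finding conditional. They do not supply the missing inputs.

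**Conclusion.** The point holds conditionally. With 50 per group, five visits to month 12, a common variance structure and missingness, and two-sided 5%, the printed 94.5% at 0.8% implies about 76% at 0.6%, or about 77–79% if the first run carried 20% loss and the second 10%. Neither Monte Carlo error nor the choice of alpha closes the gap on its own; it takes two favourable departures together to touch 80%. The statement that power stays above 80% is therefore unsupported by the inputs section 5.13 prints, and a reader cannot verify it. It is not shown to be false: a different SD or variance structure, about 10% more information, a difference of about 0.63%, or a month-9 time point for the 0.6% could each reconcile the figures.

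**What to change.** Rerun SC versus CGS with the alpha, variance components, missingness and time point used for the 94.5% figure. Replace the statement of power above 80% with the result, or with the difference detectable at 80% power. If 0.6% is the month-12 difference, the expected values are about 76–79% power, or a detectable difference of about 0.63% with the first run's standard error; the rerun decides.

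If the second simulation used other inputs or a month-9 difference, state them and reconcile the time points of the 0.6% and 0.8% differences between sections 5.8 and 5.13. In either case, print for both runs the alpha and sidedness, the intercept, slope and residual variances, the missing-data rate and pattern, and the visits used.

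The cost is one rerun, a few sentences in section 5.13 and possibly a less favourable stated figure. No extra patients are needed.

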The testing of moderators will be conducted within the IGM framework outlined above. Specifically, HbA_{1c} will be the outcome and Time will be measured in months in the level-1 model. A dummy variable indicating treatment groups will be the predictor in level-2 models. A product term of the proposed moderator and the dummy variable, together with the main effect of the moderator candidate, will be entered into the level-2 models. A significant coefficient of the product term indicates that the candidate is a significant moderator. The analysis process will be carried out using Socioeconomic Status, Family composition, adolescent age at baseline, and scores on the Diabetes Problem Solving Interview, Parent-Adolescent Relationship Questionnaire, Diabetes Family Responsibility Questionnaire, Wiebe Parental Supportive Involvement Interview, and Diabetes Responsibility and Conflict Scale separately to determine significant moderators.

To interpret the effects of any significant moderators, estimated individual growth factors (e.g., the slope in linear trajectory) will be compared among subgroups of the moderator. The analysis will reveal subgroup differences in the change of outcome due to the treatment effects. For moderators measured on continuous scales, such as adolescent age at baseline, appropriate categorization will be applied for meaningful interpretation of the findings. Important covariates will be included in the models to adjust the possible effects

[figure not shown]
of the covariates. Within this model, site differences will be treated as a between-subject covariate to adjust for its possible effects on the outcome.

Hypothesis 3b: Improvements in HbA_{1c} during the 9-month Randomized Phase will be mediated by improved scores on the Diabetes Self-Management Profile, Diabetes Responsibility and Conflict Scale, Wiebe Parental Supportive Involvement Interview, Diabetes Problem Solving Interview, and Blood Glucose Monitoring Communication Questionnaire.

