9. INCLUSION OF WOMEN AND MINORITIES

Each clinic will enroll families of about 50 eligible adolescents. The sampling plan ensures equitable representation of racial and ethnic minorities so that comparisons of minorities and non-Hispanic Caucasians are feasible. To encourage participation of minorities, we will offer evening and weekend appointments for data collection, taxi fare, meal vouchers, and reimbursement for child care to enable participation of members of minorities who are of lower socioeconomic status. Sampling objectives will ensure that the study achieves these targets: Gender: 50% male, 50% female adolescents; Children: All enrolled patients will be children; Race: 80% Caucasian; 20% African-American; Ethnicity: 90% Non-Hispanic and 10% Hispanic. The Florida and Delaware populations have become increasingly Hispanic over the past decade. The study questionnaires, informed consent and assent forms, and educational materials will be translated into Spanish by native Spanish-speaking persons and back-translated into English to ensure accurate translation. The three clinics will provide access to about 550 eligible patients, ensuring the enrollment of a diverse sample meeting these targets.

10. Targeted/Planned Enrollment Table

This report format should NOT be used for data collection from study participants.

Study Title: Clinical Use of Continuous Glucose Sensors in Adolescents with Inadequate Diabetic Control

Total Planned Enrollment: 150 parents (P) (90% of parents are expected to be female) and 150 youths (Y)

TARGETED/PLANNED ENROLLMENT: Number of Subjects (Adolescents)			
Ethnic Category	Sex/Gender		
	Females	Males	Total
Hispanic or Latino	8	7	15
Not Hispanic or Latino	67	68	135
Ethnic Category: Total of All Subjects *	75	75	150
Racial Categories			
American Indian/Alaska Native	0	0	0
Asian	0	0	0
Native Hawaiian or Other Pacific Islander	0	0	0
Black or African American	15	15	30
White	60	60	120
Racial Categories: Total of All Subjects *	75	75	150

- The "Ethnic Category: Total of All Subjects" must be equal to the "Racial Categories: Total of All Subjects."
-

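### Section 5.13 claims adequate power for all three primary hypotheses from two simulated HbA1c arm contrasts; this does not carry over to the moderator tests of Hypothesis 3a

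*Combined protocol and SAP*

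**What the plan says.** Section 5.13 sets out what was powered: "Power analysis and sample size estimation were based on projected treatment effects on HbA_{1c}, the primary outcome measure". Two contrasts are simulated.

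- CGS+BT versus CGS: "At the end of 12 months, we expect a 0.8% difference in HbA_{1c} between the CGS and CGS+BT groups". For this contrast "the Monte Carlo study with 3000 simulated samples showed that the power of the design is 94.5" percent.
- SC versus CGS: "We expect a mean difference of approximately 0.6% in HbA_{1c} between the two groups at the end of the study". Here, "with 50 participants in each group and approximately 10% missing values, the statistical power remains above 80" percent.

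The section then cites a methodological comparison in which individual growth modeling (IGM) had more power than repeated-measures ANOVA for group differences in change, and ends: "Since we will apply IGM to the evaluation of all three primary hypotheses, we are confident that the planned sample size offers sufficient statistical power".

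Hypothesis 3a (Sections 5.10 and 5.12) concerns moderation of HbA1c improvement over the 9-month Randomized Phase. Eight candidates are listed: socioeconomic status, family composition, age and five interview or questionnaire scores. Each is tested separately through a product with the treatment dummy, and the reading rule is: "A significant coefficient of the product term indicates that the candidate is a significant moderator". The general description of the level-2 models in 5.12 also gives gender and parents' marital status as examples of moderators to be tested. No interaction size, moderator distribution or power is given for any of these tests, and the plan does not label them exploratory.

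**The concern.** The closing inference of 5.13 goes from the method to the power. That IGM is more efficient than repeated-measures ANOVA for a difference between arms says nothing about how precisely a difference between two such differences can be estimated. The latter is what a product term measures, and with the same patients it is estimated with a larger standard error.

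Aim 3 depends on these tests, and 5.12 says their purpose is to find subgroups with lesser or greater benefit. If power is well below what 5.13 implies, a non-significant product term carries little information, yet the plan's own text would let it be presented as coming from an adequately powered test.

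**Working it through.** **Inputs.** From 5.13: 50 per group, a 0.8% difference at 12 months, SD 1.5% at the end of the study, five visits, stated power 94.5%. From 5.4: enrollment target of 50% boys and 50% girls. Assumed: two-sided alpha 0.05 and no multiplicity adjustment.

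**The plan's own figure.** The standardized effect is 0.8/1.5 = 0.533, as stated. A simple end-of-study comparison of two means gives 76.0% power at 50 per group, 71.6% at 45 and 66.5% at 40. The stated figure refers to a growth-model slope, so these need not match it. An analytic two-group linear growth model with five visits and SD rising from 1.2% to 1.5% gives about 67% to over 99%, depending on residual variance and intercept-slope covariance, which 5.13 does not report. With residual variance 0.2, zero covariance and 80% completing 12 months it gives 94.7%. The 94.5% is therefore attainable but cannot be confirmed, and it is accepted below.

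**Precision implied by 94.5%.** Noncentrality = 1.960 + 1.598 = 3.558. Main-effect standard error = 0.8/3.558 = 0.225% HbA1c.

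**Binary moderator, even split.** The treatment effect is estimated separately in each half of the sample, with standard error √2 × 0.225 each. Their difference has standard error √(2 + 2) × 0.225 = 0.450, twice that of the main effect.

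- 0.8% interaction: 3.558/2 = 1.779; power = Φ(1.779 − 1.960) = 42.8%.
- 0.4% interaction: 3.558/4 = 0.890; power = Φ(0.890 − 1.960) = 14.2%.
- Detectable with 80% power: (1.960 + 0.842) × 0.450 = 1.26%.
- Group size for 80% power at 0.8%: 50 × (2.802/1.779)² = about 124 per group.

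**Continuous moderator, normally distributed.** The coefficient per SD has the same standard error as the main effect, so power depends on the span over which the treatment effect changes by 0.8%.

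| Span for a 0.8% change in effect | Noncentrality | Power |
|---|---|---|
| -1 SD to +1 SD | 3.558/2 = 1.779 | 42.8% |
| Lower half to upper half (means 1.596 SD apart) | 3.558/1.596 = 2.230 | 60.6% |
| 1 SD | 3.558 | 94.5% |

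**Sensitivity, even split.** For SC versus CGS, with power taken at the 80% floor, an interaction equal to that contrast's 0.6% effect has Φ(2.802/2 − 1.960) = 28.8%. Bonferroni over the eight listed candidates lowers 42.8% to 17.0%. Section 5.9 promises a multiplicity adjustment but names no method.

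**The case against.** The strongest objection is that the result depends on the contrast. Hypothesis 3a does not say which pair of arms it concerns, and CGS+BT is also compared with SC. That effect is 0.8 + 0.6 = 1.4% from 5.13, or 9.0 − 7.4 = 1.6% from the expected means in 5.8. With the same standard error, an even-split interaction of 1.4% has power Φ(1.4/0.450 − 1.960) = about 88%, and one of 1.6% has 94.5%. This stands. A reader might infer that any interaction as large as the whole treatment effect has only 43% power, or that the detectable interaction always exceeds the effect being modified. The documents do not support either in general. Power for a fixed 0.8% interaction is nevertheless the same in every pair of arms under that standard error.

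Most listed moderators are scores or age, so the 43% depends on scaling. This also stands, and the table shows it: power is adequate only under the most favorable scaling, a full 0.8% change per SD. The even binary split is not invented, since 5.12 names gender and 5.4 targets equal numbers.

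A reader might extend the calculation to race through the 20% African-American enrollment target. Section 3.2 mentions race among background influences, but no Hypothesis 3a list includes it, nor do the moderator examples in 5.12. Section 9 concerns representation, not power.

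A reader might also infer that the plan will declare moderators absent when the product term is not significant. Section 5.12 says only what a significant term indicates. It is silent on a non-significant one, so the risk lies in that silence.

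Finally, 5.13 does disclose that power was based on HbA1c treatment effects, and no figure in it is shown to be miscalculated. That is correct. The fault is in the concluding sentence.

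**Conclusion.** The claim of adequate power for all three primary hypotheses is not supported for Hypothesis 3a. For a 0.8% HbA1c interaction, power is about 43% at an even binary split or for -1 SD versus +1 SD, and about 61% for upper versus lower half. For 0.4% at an even split it is about 14%. The interaction detectable with 80% power at an even split, about 1.26%, exceeds the two simulated effects but not the projected CGS+BT versus SC effect.

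These figures rest on the plan's unconfirmed 94.5%, an assumed two-sided alpha of 0.05 and no multiplicity adjustment. Two of these conditions probably favor the plan: the simulation uses visits to 12 months while Hypothesis 3a covers 9, and any adjustment would lower power. The simulated contrasts of Hypothesis 1 are not affected. Section 5.13 gives no power for Hypothesis 2 or the mediation tests of Hypothesis 3b either; nothing was calculated for those.

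**What to change.** - In 5.13, limit the concluding power sentence to the simulated HbA1c contrasts of Hypothesis 1, and state the alpha used.
- In 5.13, give the detectable interaction with its conditions: about 1.26% HbA1c with 80% power, for an even binary split (or -1 SD versus +1 SD), two-sided alpha 0.05, unadjusted, taking the 94.5% as given.
- In 5.12 under Hypothesis 3a, report every interaction with its 95% confidence interval, and state that a non-significant product term is not evidence of no moderation.

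The cost is wording in two sections. No patients, visits or data are added. The power claim becomes less favorable.
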